8.3.5 Regulatory reporting requirements for SAEs

- Prompt notification by the Investigator to the Sponsor of a SAE is essential so that legal obligations and ethical responsibilities towards the safety of participants and the safety of a study intervention under clinical investigation are met.
- The Sponsor has a legal responsibility to notify both the local regulatory authority and other regulatory agencies about the safety of a study intervention under clinical investigation. The Sponsor will comply with country-specific regulatory requirements relating to safety reporting to the regulatory authority, Institutional Review Boards (IRB)/Independent Ethics Committees (IEC), and Investigators.
- Investigator safety reports must be prepared for suspected unexpected serious adverse reactions (SUSARs) according to local regulatory requirements and Sponsor policy and forwarded to Investigators as necessary.
- Adverse events that are considered expected will be specified in the reference safety information (IB for tusamitamab ravtansine and SPC for ramucirumab).
- An Investigator who receives an Investigator safety report describing a SAE or other specific safety information (eg, summary or listing of SAEs) from the Sponsor will review and then file it along with the Investigator's Brochure and will notify the IRB/IEC, if appropriate according to local requirements.

8.3.6 Pregnancy

- Details of all pregnancies in female participants and, if indicated, female partners of male participants will be collected after the start of study intervention and until one year after the birth.
- If a pregnancy is reported, the Investigator should inform the Sponsor within 24 hours of learning of the pregnancy and should follow the procedures outlined in Appendix 3 ([Section 10.3](#)).
- Abnormal pregnancy outcomes (eg, spontaneous abortion, fetal death, stillbirth, congenital anomalies, ectopic pregnancy) are considered SAEs.

8.3.7 Disease-related events and/or disease-related outcomes not qualifying as AEs or SAEs

The following disease related events (DREs) are common in participants with cancer and can be serious/life threatening:

- Progression of underlying disease, as it is the study endpoint.
- Death due to progression of underlying disease, if it occurs after 30 days after the last IMP administration. All death that occurs within 30 days of the last study intervention should be reported as a SAE.

Because these events are typically associated with the disease under study, they will not be reported according to the standard process for expedited reporting of SAEs even though the event may meet the definition of a SAE. These events will be recorded on the corresponding page in the participant's eCRF within the appropriate time frame.

In case of progression of the underlying disease, with no radiologic documentation, symptoms leading to disease progression should be reported as an AE.

8.3.8 Guidelines for reporting product complaints

Any defect in the IMP/NIMP must be reported as soon as possible by the Investigator to the monitoring team that will complete a product complaint form within required timelines.

Appropriate information (eg, samples, labels or documents like pictures or photocopies) related to product identification and to the potential deficiencies may need to be gathered. The Investigator will assess whether or not the quality issue has to be reported together with an AE or SAE.

Guidance and information (contact and complaint form) are provided in the pharmacy manual and/or monitoring plan.

8.4 TREATMENT OF OVERDOSE

There is no specific antidote for treatment of overdose. In the event of an overdose, the Investigator should:

1. Contact the Medical Monitor immediately.
2. Closely monitor the participant for any AE/SAE and laboratory abnormalities.
3. Document the quantity of the excess dose as well as the duration of the overdose in the eCRF.

Decisions regarding dose interruptions or modifications will be made by the Investigator in consultation with the Medical Monitor based on the clinical evaluation of the participant.

8.5 PHARMACOKINETICS

Blood samples will be collected for the measurement of tusamitamab ravidansine and ramucirumab concentrations as described in the PK/ATA flowcharts ([Section 1.3.3](#)). The actual date and time of each sample will be recorded. Instructions for the collection and handling of PK samples will be provided by the Sponsor in a separate laboratory manual. These samples will be tested by the Sponsor's designee.

8.5.1 Non-compartmental analysis

Pharmacokinetic parameters of tusamitamab ravidansine will be calculated using non-compartmental methods from concentrations assayed in Part 1 (safety run-in). The parameters will include, but may not be limited to, those listed in [Table 13](#):

Table 13 - List of pharmacokinetic parameters and definitions

Parameters	Definition
C_{eoI}	Concentration observed at the end of IV infusion
C_{max}	Maximum concentration observed after infusion
t_{max}	Time to reach C_{max}
C_{last}	Last concentration observed above the lower limit of quantification after infusion
t_{last}	Time of C_{last}
C_{trough}	Concentration observed just before treatment administration during repeated dosing
AUC_{0-14d}	Area under the plasma concentration versus time curve calculated using the trapezoidal method from time 0 to 14 days.

Ramucirumab C_{trough} values for Part 1 and Part 2 will be reported.

8.5.2 Population approach

Data from plasma concentrations of tusamitamab ravtansine will be used for population PK analysis by non-linear mixed-effects modeling. Empirical Bayesian estimation of individual exposure parameters such as maximum concentration (C_{max}), trough concentration (C_{trough}) and area under the curve (AUC) will be derived. The population PK analysis will be reported in a standalone report (s).

8.6 PHARMACODYNAMICS

Approximately 3 mL venous blood samples for measurement of circulating CEA will be collected at prescreening, at baseline, and during the treatment period as close as possible to tumor assessments.

For CEA sample collection scheduled on the day of a treatment visit, samples should be drawn prior to initiation of ramucirumab infusion and tusamitamab ravtansine infusion.

8.7 GENETICS

Genetics are not evaluated in this study.

8.8 BIOMARKERS

Collection of samples for other biomarker research is also part of this study. The following samples for biomarker research are required and will be collected from all participants in this study as specified in the SoA:

- Tumor tissue samples will be collected and assayed for CEACAM5 expression to determine eligibility for this study.
- Blood samples will be collected for IgG measurement to explore the impact of IgG level on PK of tusamitamab ravtansine.

The level of IgG in blood drawn pre-infusion on Day 1 of Cycle 1 will be determined by a central laboratory. For this test, 2 mL of blood, corresponding to 1 mL of serum, will be collected. Instructions for the collection and handling of biological samples will be provided by the Sponsor in a separate laboratory manual. Samples may be stored for a maximum of 15 years (or according to local regulations) following the last participant's last visit for the study at a facility selected by the Sponsor to enable further analysis of biomarker responses to tusamitamab ravtansine.

8.9 IMMUNOGENICITY ASSESSMENTS

Blood samples will be collected for assessing the presence of ATA against tusamitamab ravtansine in plasma from all participants as described in the PK/ATA flowcharts (see [Section 1.3.3](#)). These samples will be tested by the Sponsor's designee.

Refer to the laboratory manual for details regarding sample collection, processing, storage, and shipment.

Plasma samples will be screened for antibodies binding to tusamitamab ravtansine and the titer of confirmed positive samples will be reported.

8.10 HEALTH ECONOMICS

Not applicable.

8.11 USE OF BIOLOGICAL SAMPLES AND DATA FOR FUTURE RESEARCH

Future research may help further the understanding of disease subtypes, disease biology, related conditions, drug response, and toxicity, and can help identify new drug targets or biomarkers that predict a patient's response to treatment. Therefore, when participants provide written consent (Appendix 1, [Section 10.1.3](#)), data and biological samples will be stored and used for future research unless prohibited by local laws or IRBs/IECs (in such a case, consent for future use of samples will not be included in the local ICF).

For participants who consent to the storage and use of their data and remaining and/or extra clinical samples, data and samples may be used after the study ends for future research related either to the drug, the mechanism of action, and the disease or its associated conditions. Such research may include, but is not limited to, performing assessments on DNA, RNA, proteins or metabolites. If future research on genetic material is performed, this will also be limited to the purpose of addressing research questions related to the drug, the mechanism of action, the disease or its associated conditions.

In the event future research is proposed to be conducted for other purposes, the study participants will be informed of those intended purposes, and will be given means to object to participation in those research projects.

Data and samples will be used in compliance with the information provided to participants in the ICF Part 2 (future research).

All study participant data and samples will be coded such that no participant direct identifiers will be linked to them. Coded data and samples may be transferred to a Sponsor site (or a subcontractor site), which may be located outside of the country where the study is conducted. The Sponsor adopts safeguards for protecting participant confidentiality and personal data ([Section 10.1.4](#)).

Samples will be stored for a maximum of 15 years after the end of the study. Any samples remaining at the end of retention period will be destroyed. If a participant requests destruction of his/her samples before the end of the retention period, the Investigator must notify the Sponsor (or its contract organization) in writing. In such a case, samples will be destroyed and related coded data will be anonymized unless otherwise required by applicable laws.

Study participants' coded data will be stored for future research for up to 25 years after the end of the study. If data are still considered of important scientific value after this period, coded data already available will be anonymized unless otherwise required by applicable laws (the same will apply to the data of a study participant who has requested the destruction of his/her samples).

Participants' coded data sets provided to researchers for a specific research project will be available to the researchers for a maximum of 2 years after the end of their specific project (end of project is defined by publication of the results or finalization of the future research project report).

9 STATISTICAL CONSIDERATIONS

9.1 STATISTICAL HYPOTHESES

The doublet cohort contains 2 parts:

Part 1 (safety run-in) aims to establish the recommended dose (RD) of tusamitamab ravidansine in combination with ramucirumab according to DLTs observed.

Part 2 is designed to obtain preliminary efficacy, safety, and PK data on tusamitamab ravidansine administered in combination with ramucirumab to participants with NSQ NSCLC. As the second part is not intended to explicitly test a hypothesis, calculations of power and Type I error were not considered in the study design.

The triplet cohort (safety run-in only) is designed to assess the tolerability and to confirm the recommended dose of tusamitamab ravidansine in combination with ramucirumab and pembrolizumab in the NSQ NSCLC population.

9.2 SAMPLE SIZE DETERMINATION

In the doublet cohort, assuming a prescreening failure rate of 80% and a study screening failure rate of 20%, approximately 225 participants will be prescreened to achieve a total of up to approximately 36 treated participants, including Part 1 (safety run-in) and Part 2.

In the triplet cohort, assuming a prescreening failure rate of 79% and a study screening failure rate of 23% based on the doublet cohort, approximately 74 participants will be prescreened to achieve a total of up to approximately 12 DLT evaluable participants.

9.2.1 Sample size for the doublet cohort, safety run-in (Part 1)

The actual sample size is expected to vary depending on DLTs observed. It is anticipated that around 6 to 12 DLT-evaluable participants will be enrolled in the safety run-in part of the cohort.

9.2.2 Sample size for the doublet cohort, Part 2

The initial plan is to treat a total of 30 participants evaluable (at least one post-baseline tumor assessment) for activity. The 6 participants treated at the recommended dose level in the safety run-in part will also be evaluable for this second part of the cohort.

Estimated ORR and 95% exact CI by numbers of responders from a sample size of 30 participants evaluable for activity are summarized in [Table 14](#).

Table 14 - Estimated objective response rate (ORR) depending on number of responders

Number of Responders (N=30)	Objective Response Rate in % (95% Clopper-Pearson CI)
6	20.00% (7.71% - 38.57%)
8	26.67% (12.28% - 45.89%)
9	30.00% (14.73% - 49.40%)
11	36.67% (19.93% - 56.14%)
12	40.00% (22.66% - 59.40%)

CI=confidence interval.

9.2.3 Sample size for the triplet cohort (safety run-in only)

The actual sample size is expected to vary depending on DLTs observed. It is anticipated that around 6 to 12 DLT evaluable participants will be enrolled in the safety run-in of the triplet cohort.

9.3 POPULATIONS FOR ANALYSES

For purposes of analysis, the following populations are defined ([Table 15](#)):

Table 15 - Populations for analyses

Population	Description
Pre-screened	All participants who signed the prescreening informed consent for CEACAM5 assay assessment of their biopsy.
Screened	All participants who signed informed consent for study participation
All-treated	All registered participants exposed to the study treatment, regardless of the amount of treatment administered. This population is the primary population for analysis of all efficacy parameters.
DLT-Evaluable	For the doublet cohort: Participants who received 2 cycles with at least 80% of the intended dose for both tasumitamab rvtansine and ramucirumab at each of the two first infusions unless they discontinued the study intervention before the end of Cycle 2 due to a DLT. For the triplet cohort: Participants who received 1 cycle with at least 80% of the intended dose for each IMP of the combination. Participants should have completed Cycle 1 unless they experienced a DLT before the end of Cycle 1.
Activity (applicable for doublet cohort only)	All treated participants who have measurable disease at study entry and at least 1 post-baseline evaluable tumor assessment. Participants with an early clinical progression or an early death due to disease progression (ie, before first planned tumor assessment) will also be included in this set. This population is the secondary population for analysis of efficacy parameters of the doublet cohort.
PK	All participants from the all-treated population who have actually received at least 1 dose or a part of a dose of tasumitamab rvtansine (SAR408701) or ramucirumab with at least 1 evaluable post-baseline concentration.
ATA	All treated participants with at least 1 post-baseline ATA result (negative, positive, or inconclusive).

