 - In the triplet cohort, tusamitamab ravtansine 150 mg/m² (or 120 mg/m², if deemed the appropriate dose by the SC) will be administered via IV infusion over 1 hour, 30 minutes on Day 1, and then every 3 weeks.
- For patients with a body surface area (BSA) >2.20 m², the dose of tusamitamab ravtansine will be calculated based on a BSA of 2.20 m².

Pembrolizumab

In the triplet cohort, pembrolizumab will be administered after ramucirumab and tusamitamab ravtansine.

- Formulation: Keytruda® (pembrolizumab) is a concentrate for solution for infusion supplied in 100 mg/4 mL (25 mg/mL) solution in single-dose vials.
- Route of administration: intravenous (IV) infusion.
- Dose regimen: pembrolizumab will be administered as a 200 mg IV infusion over 30 minutes on Day 1 and then Q3W.

Noninvestigational medicinal products:

Premedication:

Both tusamitamab ravtansine and ramucirumab have potential risk of infusion-related allergic reaction; therefore, premedication with an IV histamine H1 antagonist (diphenhydramine 50 mg IV or equivalent; eg, cetirizine, promethazine, dexchlorpheniramine, according to local approval and availability) given approximately at least 15 minutes before ramucirumab administration is required for all participants. If a participant previously experienced an infusion-related reaction (IRR) following a dose of ramucirumab or tusamitamab ravtansine, premedication for subsequent infusions will also include dexamethasone 10 mg IV and acetaminophen (paracetamol). All drugs used as premedication will be entered on the concomitant premedication page.

Statistical considerations:

- **Sample size calculations:**

This study is divided into 2 cohorts:

Doublet cohort: the cohort is divided in 2 parts: a safety run-in (Part 1) and Part 2. In the safety run-in Part, 6 to 12 DLT-evaluable participants will be enrolled in order to confirm the RP2D. In Part 2, the plan is to enroll and treat enough participants to attain a total of 30 participants evaluable for activity (ie, having at least 1 post-baseline tumor assessment). The 6 participants treated at the RP2D will also be evaluable for Part 2.

Triplet cohort: the cohort will have only 1 part: a safety run-in. 6 to 12 DLT-evaluable participants will be enrolled in order to confirm the RP2D.

- **Main analysis populations:**

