2.1 STUDY RATIONALE

Tusamitamab ravtansine is an antibody-drug conjugate (ADC) combining hu769_4D4 (SAR408377), a humanized antibody that recognizes selectively the A3-B3 extracellular domain of CEACAM5 with the potent cytotoxic maytansinoid derivative, DM4, an inhibitor of microtubule assembly. tusamitamab ravtansine is expected to selectively deliver DM4 to cancer cells expressing the CEACAM5 antigen, such as colon, stomach and its signet-ring cell subtype as well as NSQ NSCLC.

In the first-in-human monotherapy study (TED13751), the maximum tolerated dosage of tusamitamab ravtansine was identified to be 100 mg/m² every 2 weeks. Dose-limiting toxicities were mainly Grade 3 microcystic keratopathy; all were reversible. This dose is also the selected started dose for combination studies.

In the expansion phase of study TED13751, a cohort of patients with heavily pretreated NSQ NSCLC tumors testing positive for CEACAM5 ($\geq 2+$ in intensity on membranes of $\geq 50\%$ of the tumor cells) have been treated with tusamitamab ravtansine at 100 mg/m² every 2 weeks. Results from the 64 evaluable patients showed encouraging antitumor activity associated with a response rate of 20.3% (95% CI, 12.3% to 31.7%) (6).

Ramucirumab (Cyramza®); a human IgG1 monoclonal antibody that inhibits VEGFR-2 is approved in combination with docetaxel for the treatment of patients with metastatic NSCLC.

This approval was based on the results of a Phase 3 study (REVEL) a randomized placebo-controlled trial of 1,253 patients with metastatic NSCLC previously treated with a platinum-based combination therapy. Patients were randomized to receive either ramucirumab in combination with docetaxel or placebo in combination with docetaxel. The primary endpoint was overall survival (OS). Patients who received ramucirumab in combination with docetaxel had improved OS (hazard ratio: 0.86; 95% CI, 0.75 to 0.98). Median OS was 10.5 months on the ramucirumab plus docetaxel arm versus 9.1 months on the placebo plus docetaxel arm. Median progression free survival was 4.5 months for the ramucirumab arm compared to 3 months in the control arm (hazard ratio: 0.76; 95% CI, 0.68 to 0.86). Objective response rate was 22.9% for the ramucirumab arm (95% CI, 19.7% to 26.4%) compared to 13.6% in the control arm (7).

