Part 1 (Safety Run-In): In Part 1, participants will be treated with tusamitamab ravidansine and ramucirumab to assess the tolerability of the combination to be used in the subsequent part of the study. The first 3 participants will receive ramucirumab at 8 mg/kg followed by tusamitamab ravidansine at 100 mg/m^2 every 2 weeks (Q2W). Administration of tusamitamab ravidansine will begin at least 1 hour after completion of ramucirumab infusion.

The DLT observation period is the first 2 cycles (approximately 28 days). A DLT-evaluable participant must have completed 2 cycles of treatment or have been discontinued from study treatment because of a DLT; DLT non-evaluable participants will be replaced.

A minimum delay of 1 week is required between the initial dose in the first participant treated in a DL cohort and dosing the next 2 participants treated at the same DL.

- If $\leq 1/3$ participants treated at the starting dose experiences a DLT, 3 additional participants will be treated to confirm the tolerability of the combination.
 - If $\leq 1/6$ participants treated at the starting dose experiences a DLT, the starting dose will be the RP2D.
 - If $\geq 2/6$ participants treated at the starting dose experience DLTs, the dose will be de-escalated to DL -1.
- If $\geq 2/3$ participants treated at the starting dose experience DLTs, the dose will be de-escalated to DL minus 1 (DL -1).
- If ≤ 1 of the first 3 participants treated at DL -1 experiences a DLT, 3 additional participants will be treated at this DL.
 - If $\leq 1/6$ participants treated at DL -1 experiences a DLT, DL-1 will be the RP2D.
 - If $\geq 2/6$ participants treated at DL -1 experience a DLT, an alternative dosage might be considered or the doublet cohort may be stopped.
- If $\geq 2/3$ participants treated at DL -1 experience a DLT, an alternative dosage might be considered or the doublet cohort may be stopped.

Note: if $\geq 2/6$ or $\geq 2/3$ participants treated at DL -1 experience DLTs, an alternative dosage might be considered from a safety viewpoint by the Sponsor after consulting with SC. Dose reduction is shown in [Table 4](#).

Table 4 - Dose reduction for the doublet cohort Part 1 (safety run-in)

[figure not shown]
Dose level (DL)	tusamitamab rfvansine	Ramucirumab
Starting dose	100 mg/m ² Q2W	8 mg/kg Q2W
Minus -1 (DL-1)	80 mg/m ² Q2W	8 mg/kg Q2W

DL=dose level; Q2W=every 2 weeks.

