The DLT observation period is the first cycle (approximately 21 days). A DLT-evaluable participant must have completed 1 cycle of treatment or have been discontinued from study treatment because of a DLT. DLT non-evaluable participants will be replaced.

A minimum delay of 1 week is required between the initial dose in the first participant treated in a DL cohort and dosing the next 2 participants treated at the same DL.

- If $\leq 1/3$ participants treated at the starting dose experiences a DLT, 3 additional participants will be treated to confirm the tolerability of the combination.
 - If $\leq 1/6$ participants treated at the starting dose experiences a DLT, the starting dose will be the RP2D.
 - If $\geq 2/6$ participants treated at the starting dose experience DLTs, the dose will be de-escalated to DL -1.
- If $\geq 2/3$ participants treated at the starting dose experience DLTs, the dose will be de-escalated to DL minus 1 (DL -1).
 - If $\leq 1/6$ participants treated at DL -1 experiences a DLT, DL-1 will be the RP2D.
 - If $\geq 2/6$ participants treated at DL -1 experience a DLT, an alternative dosage might be considered or the triplet cohort may be stopped.
- If $\geq 2/3$ participants treated at DL -1 experience a DLT, an alternative dosage might be considered or the triplet cohort may be stopped.

Note: if $\geq 2/6$ or $\geq 2/3$ participants treated at DL -1 experience DLTs, an alternative dosage might be considered from a safety viewpoint by the Sponsor after consulting with SC. Dose reduction is shown in [Table 6](#).

Table 6 - Dose reduction for the triplet cohort

[figure not shown]
Dose level (DL)	tusamitamab ravidansine	ramucirumab	pembrolizumab
Starting dose	150 mg/m ² Q3W	10 mg/kg Q3W	200 mg Q3W
Minus -1 (DL-1)	120 mg/m ² Q3W	10 mg/kg Q3W	200 mg Q3W

DL=dose level; Q3W=every 3 weeks.

Infusion of tusamitamab ravidansine will be administered at least 1 hour after the end of ramucirumab infusion. For patients with a BSA >2.20 m², the tusamitamab ravidansine dose will be calculated based on a BSA of 2.20 m².

The decision tree for doses for triplet cohort is summarized in [Figure 5](#).

Figure 5 - Decision tree for the triplet cohort for tusamitamab ravidansine

*Note: In case of 2 or more DLTs at DL -1, the cohort may be stopped or the dosage reconsidered.

Abbreviations: DL -1=dose level -1 (120 mg/m²); DLT=dose-limiting toxicity; RP2D=recommended dose.

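### Triplet Table 15 literally makes a participant non-evaluable when a DLT interrupts Day 1 dosing, and the doublet SAP states two different DLT exemptions

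*Protocol*

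**What the plan says.** **Triplet.** Protocol Section 9.3, Table 15, repeated in the synopsis, uses two sentences. The first sets the dose condition: "Participants who received 1 cycle with at least 80% of the intended dose for each IMP of the combination". The second sets completion and carries the only DLT exemption: "Participants should have completed Cycle 1 unless they experienced a DLT before the end of Cycle 1". Section 4.1 says a DLT-evaluable participant "must have completed 1 cycle of treatment or have been discontinued from study treatment because of a DLT", and that non-evaluable participants are replaced. SAP Section 1.1 states that the SAP does not cover this cohort, which had not started.

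**Doublet.** Table 15, the synopsis and SAP Table 5 require at least 80% of both drugs at each of the first two infusions "unless they discontinued the study intervention before the end of Cycle 2 due to a DLT". The operational paragraph under SAP Table 5 instead includes participants with a DLT in the observation period that the Study Committee has validated, and does not ask for discontinuation. It also excludes participants overdosed by 30% or more. Section 4.1 says a participant "must have completed 2 cycles of treatment or have been discontinued from study treatment because of a DLT; DLT non-evaluable participants will be replaced", and does not mention the 80% condition.

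**Use of the population.** Protocol Section 9.4.2.1 summarizes in-window DLTs on the DLT-evaluable population. Only events meeting the DLT criteria in later cycles are summarized on the all-treated population. SAP Section 4.7.2 lists in-window DLTs in the DLT-evaluable population.

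**The concern.** A dose-received condition exists to remove participants who had too little exposure to reveal toxicity. Someone who has already had a DLT has given the answer, so low exposure is no reason to set that person aside, least of all when the DLT caused it. On its wording, the triplet definition does set such a person aside.

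DLT incidence is the primary endpoint of doublet Part 1 and of the triplet. For the doublet, SAP Section 4.3.2.1 defines no intercurrent-event strategy because the population definition is taken to rule such events out. The definition therefore carries the estimand. A DLT removed at that step is missing from the primary summary, and the participant's place may go to someone without a DLT. The bias runs one way, towards a lower reported rate.

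**Working it through.** **1. The plan's own figure.** The one stated number built on the DLT-evaluable count is the triplet prescreening total (Section 9.2: 12 evaluable, failure rates 79% and 23%). 12 / ((1 − 0.79) × (1 − 0.23)) = 12 / (0.21 × 0.77) = 74.2, against about 74 stated. It reproduces, and this point does not change it.

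**2. Triplet case, step by step.** Inputs:
- Section 4.1, Table 5: a Grade 4 non-hematologic event is a DLT.
- Section 6.1: ramucirumab is given first, then tusamitamab ravtansine at least 1 hour later, then pembrolizumab, all on Day 1.
- Appendix 4: a Grade 3-4 infusion-related reaction to ramucirumab interrupts that infusion and ends ramucirumab for good.

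Take a Grade 4 reaction that stops the ramucirumab infusion before 80% has been given.
- Dose sentence of Table 15: not met, and it contains no exemption.
- Completion sentence: waived, because a DLT occurred.
- Both are required, so the participant is not DLT-evaluable.
- Section 4.1: replaced.
- Section 9.4.2.1: absent from the in-window DLT summary, and not picked up by the all-treated summary of later cycles.
- Sections 8.3.1 and 9.4.2.2: still present in the all-treated TEAE and AESI tables, since every protocol-defined DLT is an AESI.

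**3. Doublet case.** Take a confirmed DLT with under 80% of one drug at one of the first two infusions and treatment not discontinued.

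| Text | Status |
|---|---|
| Protocol Table 15, synopsis, SAP Table 5 | Not evaluable |
| SAP Section 3 operational paragraph | Evaluable |
| Protocol Section 4.1 | Its stated condition is met if two cycles were completed |

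The anticipated DLT is corneal, and in the first-in-human study "Dose-limiting toxicities were mainly Grade 3 microcystic keratopathy; all were reversible". Appendix 4 handles a first Grade 3 keratopathy by omitting tusamitamab ravtansine and restarting it at a reduced dose while ramucirumab continues, so nothing is discontinued. The reduced dose is 80/100 = 80% of the starting dose, which satisfies a condition of at least 80%. The case therefore fails Table 15 only if the first two infusions means the scheduled Cycle 1 and Cycle 2 infusions, which the documents do not state.

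**4. Size if it happens once.** Suppose two participants at a dose level have a DLT. With both counted among six evaluable, the rate is 2/6 = 33.3% (Clopper-Pearson 95% CI 4.3% to 77.7%). If one is dropped and replaced by a participant without a DLT, it is 1/6 = 16.7% (0.4% to 64.1%). The plan specifies only descriptive statistics for DLTs; the intervals are given here for scale.

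**The case against.** The strongest reply has four parts.

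*The two triplet sentences belong together.* They are adjacent, and the exemption may have been meant for both. That is plausible, but the wording does not say it and no SAP settles it.

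*The doublet is already handled.* The operational paragraph implements SAP Table 5 and keeps validated DLTs. This stands. A reader might infer that doublet DLTs will be lost; if that paragraph is followed, the 80% condition loses none. What remains is a table and a paragraph in the same SAP section that disagree.

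*Section 4.1 is not a rival rule.* A reader might count it as a further conflicting definition because it omits the 80% condition. It says what a participant must have done, which is a necessary condition and can hold alongside a dose condition. It is a shorter statement to be aligned, not a proven contradiction.

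*The dose decision is not affected.* Since 2/6 and 1/6 fall on opposite sides of the de-escalation boundary, a reader might infer that the RP2D could be wrong. The documents do not show this. The rules count participants treated, not evaluable (at most 1 of 6 "participants treated at the starting dose experiences a DLT, the starting dose will be the RP2D"), and under Sections 4.1 and 10.1.5 the Study Committee confirms DLTs and makes the decision with the data before it. The synopsis does speak of evaluable participants ("6 to 12 DLT-evaluable participants will be enrolled in order to confirm the RP2D"), and replacement points the same way, so the link is loose. Loose wording is not evidence that a confirmed DLT would be ignored.

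**Conclusion.** The point holds as a minor one. In the triplet, the literal definition can remove a DLT from the primary DLT summary, and nothing yet written corrects it. In the doublet, the SAP contradicts itself about who is exempt, without loss if its operational paragraph governs.

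The direction is certain: dropping a DLT case lowers the reported rate, by 16.7 percentage points in the 2/6 to 1/6 example. The frequency cannot be estimated from the documents, which give neither a DLT rate nor a share of DLTs that interrupt dosing. It is probably small, because all triplet drugs are given on Day 1 and only a DLT during that dosing is affected. The conclusion rests on reading the two triplet sentences as separate conditions. It concerns the reported endpoint only: the event would remain visible elsewhere in the safety tables, and no change to the RP2D is claimed.

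**What to change.** In protocol Table 15, the synopsis, SAP Table 5 and the future triplet SAP, state that a participant with a Study Committee-confirmed DLT in the observation window is DLT-evaluable and not replaced, whatever percentage of dose was received and whether or not treatment was discontinued. Apply the 80% and completion conditions only to participants without a DLT.

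Align Section 4.1 and the SAP Section 3 operational paragraph with that rule. In doing so, say whether the first two infusions are those scheduled or those given, and whether the overdose exclusion still applies to a participant with a DLT.

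Add one listing of all in-window DLTs in the all-treated population, so that no case depends on the evaluability call to be seen.

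The cost is wording and one listing, with no new data. The reported DLT rate may be slightly less favourable. Protocol Section 9.4 leaves the description of populations to the SAP, so the triplet rule is best settled there before that run-in begins.
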